**1. Purpose and Objectives:**

This protocol does not include any administration of medication or other interventions. This protocol will record cognitive performance and decision-making behavior in Veterans who seek mental health services in the substance use disorder intensive outpatient program (IOP). The goal is to identify the neurobehavioral effects of a structured, brief cognitive-based psychotherapy currently being conducted in the IOP along with other supportive, unstructured, treatments. The benefit of this study will be to obtain a better understanding of neurobehavioral changes occurring from evidence-informed treatments.

Aim 1: To determine if measurable neurobehavioral function in the domains of problem solving, decision making, and motoric impulsivity is predictive of treatment success and adherence outcomes (e.g. Urinary Drug Screen/Breathalyzer Analysis results, appointment no shows, early drop out, recidivism).

Exploratory Aim: To determine if there are between group differences in neurobehavioral function as a result of treatment modality being received as standard of care in the substance use outpatient setting.

**2. Background, Significance, and Scientific Rationale:**

It is established that impulsivity is a tremendous risk factor for the development of addiction (Bickel et al., 2007) and for treatment failure (Loree, Lundahl, & Ledgerwood, 2015). Impulsivity is a multi-faceted trait that has been conceptually divided into a more decision-based domain and rapid “acting without thinking” motoric domain(Swann, [name], Moeller, & Dougherty, 2002), where greater impulsivity in both domains has been found in patients addicted to stimulants in particular (Ahn & Vassileva, 2016). Trait personality measures of impulsivity typically capture some elements of both domains and frequently correlate poorly with individual task metrics of impulsivity. Therefore, comprehensive assessment of cognitive change (as it may underlie improvements in mental perseverance and thus changes in substance use) should include objective behavioral measures of both decision-making and motoric impulsivity. The addition of focused neurocognitive tasks holds potential to *identify mechanisms of* psychotherapy effects, such as whether a structured cognitive behavioral therapy may reduce substance use by promoting mindful attention generally, or whether it influences future-orientation specifically.

There are currently multiple treatments being conducted in the IOP clinic as standard of care, with a particular psychotherapy of interest for this study being a brief, structured cognitive-based treatment, called the Mind Freedom Plan (MFP). This treatment is one of two treatments being administered, with the other being a supportive, unstructured treatment that is also provided as standard of care. The aim of the MFP treatment is to improve problem solving abilities, increase engagement in pleasurable activities, and teach the patient to identify and change maladaptive thoughts. Structured worksheets for each session have been developed for

the purpose of achieving these goals. An exploratory aim of the current study will be to identify whether there are neurobehavioral differences in subjects as a result of the treatment modality being conducted during their treatment regimen. This is novel due to the lack of studies previously examining neurobehavioral impulsivity tasks as a metric for exploring differences in treatment modality.

The VA has an increasing need for brief, efficacious interventions to assist Veterans in reducing alcohol and substance abuse. The emphasis on brief therapies is partly due to VA initiatives and ongoing access concerns that have limited the number of sessions providers are allotted with patients. Additionally, there are significant efforts to roll out and integrate evidence based practices across the VA. This exploratory aim will be an effort to meet the intersection of these demands by examining a brief evidence-informed therapy for substance users in outpatient treatment. The focus of this aim will be to determine whether this treatment results in measurable changes in neurobehavioral performance shown to be aberrant in addiction. These behaviors might serve as *early-indicator proxy markers* for improvement in cognitive domains relevant to addiction, which could in turn result in longer-term benefits of alcohol or drug abstinence.

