### **3. Study Design:**

This protocol will recruit approximately 35 Veterans once they enroll in the McGuire VA Medical Center Substance Abuse Treatment Program (SATP) IOP to complete two sessions of questionnaires and neurobehavioral measures, lasting approximately 3 hours in total. Each subject will meet initially with research staff after their SATP intake (conducted as standard of care), but prior to initiating treatment for the first session. Subjects will then meet with research staff again approximately one month later following their completion (or potentially incompletion) of the treatment. Following this meeting, research staff will complete a targeted CPRS medical chart review to collect information on appointment no shows, early termination of services, and results of Urinary Drug Screen (UDS) and Breathalyzer collections, and results of the Beck Depression Scale and Quality of Life Inventory administered during the SATP intake. 90 days following this chart review, a second chart review will occur to collect the same information, if available, for the post-treatment time period, along with information about whether they have re-entered treatment.

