### **4. Methods:**

#### **a. Procedures:**

The study will take place at the Substance Abuse Rehabilitation Program-Intensive Outpatient Program (IOP) of the Richmond VA Medical Center (RICVAMC). To minimize subject burden, consent and the first visit testing procedures will take place in the same visit to RICVAMC if possible. The study entails two visits with study staff. The first visit will include retrieving informed consent, and once enrolled, the completion of several questionnaires (see below). This visit is expected to last 60-90 minutes. The subject will then be scheduled for a follow up visit in to be conducted after he/she completes the intensive outpatient substance use program. This visit will last approximately 2 hours, and will involve questionnaires and desktop performance based tasks (see below)

**CPRS Chart Review.** CPRS records will first be reviewed by research study staff (research assistants) for intake and progress notes pertaining to the entry into IOP. When a Veteran is

identified to be entering the program and is determined to not have legal involvement from examining the intake, the Veteran will be contacted by research staff in a face-to-face encounter in the SATP clinic to explore his/her interest in participating in the current study. If interested, an appointment will be scheduled to meet to complete informed consent and the initial self-report tests. For the purposes of this study, legal involvement will be defined as a current legal issue identified during the clinic screening that mandates the completion of a substance use treatment program.

Once a subject has consented and is confirmed eligible to participate in the protocol, he or she will be assigned a five-digit ID number for this protocol. The subject will be identified by this number on all study forms, questionnaires, and surveys. The file that links a subject's name and other personally-identifiable information to this ID code number will be an electronic excel file on a password-protected virtual drive furnished by VA.

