**b. Data**

The study features a series of questionnaires in the initial visit, and a combination of questionnaires alternating with desktop behavioral tests during the second visit. Below are the descriptions of each measure:

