#### Data Analysis

The analytic plan includes conducting an independent-group t-test of each of the following continuous dependent variables, or chi-square for categorical dependent variables: 1)

proportion drug-free urines; 2) retention in program (Chi-Square); 3) Quality of life score on the QOLI; 4) Delay discounting constant k; 5) Stop signal reaction time (SSRT) on the stop-signal task; 7) Reaction time in the Emotional Go-NoGo task, 8) errors in the DKEFS Tower Test.

A repeated-measures design will be used to examine the within-subjects effects of the treatments on state depression and quality of life, as well as for a group X treatment interaction effect. Although we do not expect an intervention of this time scale of to alter trait impulsivity, we will also analyze within-subject changes in BIS11 scores as an exploratory analysis. Lastly, a between-group design comparing the MFP group vs. TAU group for substance use primary outcomes of symptomology and neurobehavioral measures for problem solving and impulsivity. Individual differences in PTSD and anxiety measures and other symptomatology will be included as covariates to account for confounding factors in the analyses.

c. Facilities and Resources

The consent procedures and behavioral testing of this protocol will take place in the new second-floor Mental Health services facility at RICVAMC. Written informed consent procedures and clinical interviewing will take place in private interview rooms of this new second-floor RICVAMC wing. Questionnaires and laboratory behavioral tasks will be administered at dedicated research task workstations installed in testing rooms.

d. Staff Qualifications

*[name].* will be the Principal Investigator of this protocol. [name] has a 5/8 VA appointment and a joint (faculty) appointment as Associate Professor of Psychiatry at Virginia Commonwealth University. He has extensive experience in the laboratory testing of impulse control and decision-making in addicted inpatients, outpatients, and at-risk human subjects. He is also known for his successful design and execution of protocols to examine the neurocircuitry of motivation and self-control in addicted and adolescent at-risk populations. He has over 50 peer-reviewed publications and book chapters, 48 of which are available in PUBMED.

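### The rationale and the benefit statement speak of neurobehavioral change from treatment, but each performance task is given only once, after treatment, so the data support only post-treatment differences between MFP and TAU.

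*Protocol*

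**What the plan says.** Three statements set out what the study is meant to learn from the neurobehavioral measures.

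- Section 1 (Purpose and Objectives), benefit sentence: the study is to "obtain a better understanding of neurobehavioral changes occurring from evidence-informed treatments".
- Section 1, Exploratory Aim: "To determine if there are between group differences in neurobehavioral function as a result of treatment modality".
- Section 2 (Background), on the same aim: its focus is to "determine whether this treatment results in measurable changes in neurobehavioral performance shown to be aberrant in addiction". The section adds that these behaviors might serve as early proxy markers of improvement.

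On timing, section 3 (Study Design) refers to "two sessions of questionnaires and neurobehavioral measures". Section 4a (Procedures) is more specific: "The first visit will include retrieving informed consent, and once enrolled, the completion of several questionnaires". Section 4b (Data) describes "a series of questionnaires in the initial visit, and a combination of questionnaires alternating with desktop behavioral tests during the second visit". The measure descriptions place the Tower Test and the three computer tasks under Visit Two. The project timeline shows four self-report scales at Day -7 to Day -1 and the three computer tasks at Day 29 to Day 35.

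Under Data Analysis, delay discounting, stop-signal, Go-NoGo and Tower Test outcomes are compared by independent-group t-test, and the section ends with "a between-group design comparing the MFP group vs. TAU group for substance use primary outcomes of symptomology and neurobehavioral measures". Within-subject analyses are planned for depression and quality of life and, as exploratory, the BIS-11. None is planned for a performance task.

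**The concern.** A claim that treatment changed performance needs a value before treatment, or at least a reference group whose course is known. Neither exists for the four tasks. There is no pre-treatment administration, and the comparison group is itself in active care: it receives supportive therapy within the same outpatient program.

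What is at stake is the conclusion the study may draw. If the rationale and benefit sentences stand, a difference seen once, after treatment, could be written up as a neurobehavioral improvement produced by MFP, or used to present the tasks as early markers of improvement. A null result could likewise be read as showing that treatment does not alter these functions. The schedule supports neither statement. Aim 1, on prediction of treatment success and adherence, is outside this point.

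**Working it through.** The protocol gives no power, effect-size or precision figure for these measures, so there is nothing to reproduce. The check is of timing first, then of what a single post-treatment value can identify.

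**Step 1. Count the administrations** (sections 4a and 4b, measure descriptions, timeline).

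| Measure | Before treatment | After treatment |
|---|---|---|
| Delay discounting | none | once, Visit 2 |
| Stop-signal | none | once, Visit 2 |
| Emotional Go-NoGo | none | once, Visit 2 |
| Tower Test | none | once, Visit 2 (measure description; not in the timeline) |
| BIS-11 | Visit 1 | Visit 2 |
| QOLI | intake, from chart | Visit 2 |
| BDI | intake, from chart | Visit 2 (measure description; timeline lists only the chart value) |

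So 0 of 4 performance tasks have a pre-treatment value. The Study Design phrase is the only text that could suggest otherwise, and no detailed listing bears it out.

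**Step 2. What the comparison identifies.** Write the mean task score in each group as pre and post. The observed contrast is

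D = post(MFP) − post(TAU).

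If assignment is random, the expected pre values are equal, so in expectation

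D = change(MFP) − change(TAU).

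D is therefore a valid between-modality contrast, but the two changes are not separately identified. Score the task so that higher is better and suppose D = 0.5 SD (illustrative). The same D arises from:

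- change(MFP) = 0.5 and change(TAU) = 0: MFP improved;
- change(MFP) = 0 and change(TAU) = −0.5: TAU worsened;
- change(MFP) = 1.0 and change(TAU) = 0.5: both improved.

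D = 0 fits both groups improving equally, neither moving, or both worsening equally. This does not depend on the number of Veterans.

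**Step 3. Precision at about 35 Veterans** (context only). The inputs are N = 35 from Study Design and an assumed split, since the protocol gives no ratio. The standard error of a difference in means, in SD units, is sqrt(1/n1 + 1/n2).

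- 1:1 split: sqrt(1/17.5 + 1/17.5) = 0.338; 95% half-width 1.96 × 0.338 = 0.66.
- 2:1 split (assumed because Recruitment describes two MFP providers and a different provider for supportive therapy): sqrt(1/23.33 + 1/11.67) = 0.359; 95% half-width 1.96 × 0.359 = 0.70.

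At an assumed two-sided alpha of 0.05 and 80% power, with all 35 analysed and a normal approximation, the detectable post-treatment difference is (1.960 + 0.842) × 0.338 = 0.95 SD (1:1), or 2.802 × 0.359 = 1.00 SD with the unrounded standard error (2:1).

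**Step 4. What Visit 1 BIS-11 could add as a covariate.** Adjustment multiplies the standard error by sqrt(1 − rho²). Section 2 says trait scales often correlate poorly with task metrics. At an assumed rho of 0.2 to 0.3 the factor is sqrt(1 − 0.04) = 0.98 to sqrt(1 − 0.09) = 0.95, a reduction of 2 to 5%. It gives no information on task change or its direction.

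**The case against.** The best defence is that the formal Exploratory Aim asks only for between-group differences, and section 2 repeats it in those terms elsewhere. Section 7 (Recruitment) says Veterans are randomly assigned to a provider, and the provider determines MFP or supportive therapy. With true randomization and adequate follow-up, a post-only comparison estimates the effect of one modality relative to the other. It could even be argued that causing change means no more than this relative effect. Most of this stands: the aim and the planned test agree, and the comparison is not invalid for want of a baseline. What it does not rescue is the benefit sentence, which speaks of changes from treatments in the plural, or the focus sentence in section 2, which is tied to improvement in domains described as aberrant. Both need a direction within a group. The proxy-marker remark is hedged and is motivation rather than a planned conclusion, but it too rests on improvement.

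A reader might also infer that chance baseline differences at this sample size are a bias left uncorrected. The documents do not support that. Under random assignment, the 0.34 SD figure is ordinary sampling error, already contained in the t-test's standard error. Data Analysis also plans PTSD, anxiety and other symptom measures as covariates. The figure shows low precision and nothing more.

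Nor does the protocol say that a post-only difference will be reported as change. That is a risk created by the wording, not a stated rule.

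**Conclusion.** The point holds as a mismatch between two statements and the schedule. The focus sentence in section 2 and the benefit sentence in section 1 claim change in neurobehavioral performance, while all four tasks are measured once, after treatment, and compared only between groups. Within-person change is not estimable for any of the four.

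What remains available is a post-treatment MFP versus TAU difference. It rests on two conditions: that the clinic's provider assignment is truly random, on which the protocol gives little detail, and that enough Veterans return for Visit 2. The second matters because task values exist only for those who return, and without a task baseline selective loss on these measures cannot be examined. Under the assumed splits, that difference would carry a 95% half-width of about 0.66 to 0.70 SD.

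The fault does not extend to the wording of the Exploratory Aim or to the self-report measures with pre and post values. It is a correction to what may be concluded, worth making because it costs almost nothing.

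**What to change.** 1. In the benefit sentence of section 1 and the focus sentence of section 2, limit the conclusions for the four tasks to differences in post-treatment neurobehavioral function between MFP and TAU. Leave the proxy-marker idea as background, not as something these data can establish.
2. Keep change language only for measures with pre and post values: BIS-11, and BDI and QOLI using the intake chart values.
3. Reconcile the Study Design description of the two sessions with Procedures, Data and the timeline, so that the tasks appear at the second visit only. Add the Tower Test and the Visit 2 BDI-II to the timeline.
4. Optionally, name Visit 1 BIS-11 among the covariates for the task comparisons, described as a small precision gain and not as a substitute for a task baseline.

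The cost is a few sentences and, if wanted, one covariate already collected. No visit or procedure is added. The price is a more modest claim. Keeping the claim of change would instead require the tasks at Visit 1 as well, with added burden and attention to practice effects.

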### **3. Study Design:**

This protocol will recruit approximately 35 Veterans once they enroll in the McGuire VA Medical Center Substance Abuse Treatment Program (SATP) IOP to complete two sessions of questionnaires and neurobehavioral measures, lasting approximately 3 hours in total. Each subject will meet initially with research staff after their SATP intake (conducted as standard of care), but prior to initiating treatment for the first session. Subjects will then meet with research staff again approximately one month later following their completion (or potentially incompletion) of the treatment. Following this meeting, research staff will complete a targeted CPRS medical chart review to collect information on appointment no shows, early termination of services, and results of Urinary Drug Screen (UDS) and Breathalyzer collections, and results of the Beck Depression Scale and Quality of Life Inventory administered during the SATP intake. 90 days following this chart review, a second chart review will occur to collect the same information, if available, for the post-treatment time period, along with information about whether they have re-entered treatment.

### **4. Methods:**

#### **a. Procedures:**

The study will take place at the Substance Abuse Rehabilitation Program-Intensive Outpatient Program (IOP) of the Richmond VA Medical Center (RICVAMC). To minimize subject burden, consent and the first visit testing procedures will take place in the same visit to RICVAMC if possible. The study entails two visits with study staff. The first visit will include retrieving informed consent, and once enrolled, the completion of several questionnaires (see below). This visit is expected to last 60-90 minutes. The subject will then be scheduled for a follow up visit in to be conducted after he/she completes the intensive outpatient substance use program. This visit will last approximately 2 hours, and will involve questionnaires and desktop performance based tasks (see below)

**CPRS Chart Review.** CPRS records will first be reviewed by research study staff (research assistants) for intake and progress notes pertaining to the entry into IOP. When a Veteran is

identified to be entering the program and is determined to not have legal involvement from examining the intake, the Veteran will be contacted by research staff in a face-to-face encounter in the SATP clinic to explore his/her interest in participating in the current study. If interested, an appointment will be scheduled to meet to complete informed consent and the initial self-report tests. For the purposes of this study, legal involvement will be defined as a current legal issue identified during the clinic screening that mandates the completion of a substance use treatment program.

Once a subject has consented and is confirmed eligible to participate in the protocol, he or she will be assigned a five-digit ID number for this protocol. The subject will be identified by this number on all study forms, questionnaires, and surveys. The file that links a subject's name and other personally-identifiable information to this ID code number will be an electronic excel file on a password-protected virtual drive furnished by VA.

CPRS will also be used to complete a review following the second visit with subjects to collect information on appointment no shows, early termination of services, results of Urinary Drug Screen (UDS) and Breathalyzer collections, and results of the Beck Depression Inventory and Quality of Life Inventory administered during the SATP intake. 90 days following this chart review, a second chart review will occur to collect the same information, if available, for the post-treatment time period, along with information about whether they have re-entered treatment.

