*Adjusting Delay Discounting (DD) Task* - This decision task assesses how a subject de-values a hypothetical money reward the longer he or she would have to wait to receive it (“delay-discounting”). The participant chooses between immediate adjusting rewards (e.g., “\$5 now”), and delayed rewards (e.g., “\$10 in 1 week”). Participants are exposed to a series of choices where the future reward magnitudes are \$10, \$25, \$100, \$250, \$1000 or \$2500 (for delayed rewards) at delay periods of 1 day, 1 week, 1 month, 6 months, 1 year, 5 years or 25 years. The computer program varies the choices available across trials according to an algorithm that rapidly converges on an indifference point for each delay interval for every reward amount. These indifference points enable calculation of a single constant (“K”) that characterizes the severity of DD for that subject. The task ends once indifference points have been determined for each magnitude at each delay, usually within four minutes. Two different question series will be administered, one series involving smaller dollar amounts (per above), and another series involving much higher amounts (e.g. \$50,000) in order to assess individual differences in the reduction of delay-discounting severity typically observed when subjects consider very high hypothetical reward magnitudes. We hypothesize that subjects who do not adhere to treatment will devalue delayed rewards more severely, and will not show as great a reduction in discounting

when very large hypothetical rewards are presented. This task requires approximately 15 minutes.

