**Stop-Signal Task (SST)** - In this rapid-response impulsivity task, participants view a series of go stimuli ("X" or "O") in the center of the screen and are told to press the keyboard left arrow button when they saw an "X" and to press the right arrow button when they see an "O". On a subset of trials, a stop-signal (a 500 Hz tone presented for 250ms) is presented as a short delay after the go stimulus. Participants are instructed to respond as quickly and accurately as possible, but to withhold their response on Stop trials (on trials with the tone). The delay of the onset of the stop-signal is dynamically titrated by 50 ms intervals to promote a 50% rate of successful stops. The Stop Signal Reaction Time (SSRT) will be calculated as the interval between "go" and subsequent "stop" signals at which the subject can stop half the time. We hypothesize that subjects who do not adhere to treatment will show a faster SSRT, meaning that their response style is more "ballistic," and difficult to stop once-launched. This task requires approximately 12 minutes.

**The Emotional Go-NoGo Task** – This task presents a series of facial stimuli with either no facial expression, or with expression of an emotion, for 500 ms each, atop a black screen. A white fixation crosshair is displayed between Face stimuli. Facial stimuli are composed of sets of multiple faces of each of several actors/models, across neutral and different emotions. The subject is to respond with a keyboard or mouse press when he or she sees either a neutral face (neutral blocks) or an emotional face (emotion blocks). Blocks of trials are set in pairs, where at the start of one block, subjects are instructed on-screen that the emotional face is the target (to which to respond) and the neutral face is the non-target, and at the start of the counterpart block, the reverse instruction holds true in the other block. Attentional capture by either positive or negative emotions will be indexed by the rate of commission errors to emotion non-target faces relative to commission errors to neutral non-target faces. The task lasts roughly 14 minutes, including self-paced rest breaks between blocks.

Project timeline (Day 0 is the first day of IOP)		
Timeline	Study activities	Measures

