Day -7 – Day -1	
 
- Contact with potential subjects for recruitment during a face to face meeting when they are in the SATP clinic
 
- Consent and pre-treatment baseline assessment
 
	Brief Addiction Monitor (BAM), Barrett Impulsivity Scale-11 (BIS-11), Posttraumatic Checklist-5 (PCL-5), Beck's Anxiety Inventory
Day 0 – Day 28	
 
- Participants engage in either MFP or TAU treatment during their IOP engagement
 
	N/A
Day 29 – Day 35	
 
- Post-treatment assessment
 
- Chart review: treatment engagement (appointment no shows, early drop out) and Breathalyzer/UDS results, results of Beck Depression Inventory and Quality of Life Inventory.
 
	BIS-11, Delay Discounting Task, Stop-Signal Task, Emotional Go-NoGo task, Quality of Life Inventory
Day 120	
 
- Chart Review: recidivism (treatment re-entry) and Breathalyzer/UDS results
 
	N/A

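### The protocol gives conflicting rules for Visit 2, the only visit with performance tasks; the Procedures wording makes no provision for Veterans who leave the IOP early

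*Protocol*

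**What the plan says.** Three places in the protocol set the timing of the second visit.

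- **Section 4.a, Procedures:** the follow-up visit is to be "conducted after he/she completes the intensive outpatient substance use program". Non-completers are not mentioned.
- **Section 3, Study Design:** subjects meet staff again "approximately one month later following their completion (or potentially incompletion) of the treatment".
- **Project timeline in section 4.b:** the row for Day 29 to Day 35 is labelled "Post-treatment assessment". The table header states that "Day 0 is the first day of IOP". No completion condition is attached.

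Section 4.b says where the tasks sit: questionnaires at the first visit, and "a combination of questionnaires alternating with desktop behavioral tests during the second visit". Delay discounting, stop-signal, Emotional Go-NoGo and the Tower Test are all described under Visit Two.

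Aim 1 in section 1 asks whether performance in these domains predicts treatment success and adherence. Its examples are drug-screen and breathalyzer results and "appointment no shows, early drop out, recidivism". The delay-discounting description expects that "subjects who do not adhere to treatment will devalue delayed rewards more severely". The stop-signal description states a matching hypothesis about non-adherent subjects, and the Tower description links errors to poorer adherence.

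**The concern.** The three statements agree for a Veteran who finishes the four-week program on schedule. They differ for one who leaves, say, in week 2. Section 3 provides explicitly for a second visit, the timeline's fixed window is consistent with one, and section 4.a provides for none.

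A missed second visit cannot be made good from other data, because no task is given earlier. Aim 1 names early drop-out as an outcome, so testing that part needs task scores from Veterans who dropped out as well as from those who stayed. If the visit is reserved in practice for completers, that comparison has one empty group. The remaining adherence outcomes are then studied only among Veterans who stayed to the end, which narrows the range of adherence on which any association depends.

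**Working it through.** There is no figure in the protocol to reproduce. It gives a target of approximately 35 Veterans (section 3) and no drop-out rate, significance level, power or effect size. The check is therefore a comparison of the texts, followed by an illustration on stated assumptions.

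**Step 1. The rules side by side**

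| Veteran | Section 4.a | Section 3 | Timeline |
|---|---|---|---|
| Completes in four weeks | Visit after completion | Visit at about one month | Visit Day 29 to 35 |
| Leaves early | No visit provided for | Visit at about one month | Visit Day 29 to 35, no condition stated |

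Only section 3 says outright that non-completion is allowed. The timeline supports it by giving a fixed window.

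**Step 2. Is there another source of task scores?** Section 3 speaks loosely of two sessions of questionnaires and neurobehavioral measures. The itemised lists in section 4.b and the timeline place every performance task at the second visit and only questionnaires at the first. So there is no other source.

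**Step 3. Which parts of Aim 1 depend on the rule?** Under the literal section 4.a rule:

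- Early drop-out: every scored Veteran is a completer, so there is no contrast.
- No-shows, drug-screen and breathalyzer results, treatment re-entry: these still vary among completers, so they can be analysed, but in a selected sample.
- Retention as listed in the Data Analysis section: this is a chart variable and needs no task score.

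**Step 4. Illustrative size.** Number unscored under section 4.a = 35 × assumed drop-out share.

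- 20%: 35 × 0.20 = 7 unscored, 28 scored
- 40%: 35 × 0.40 = 14 unscored, 21 scored

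The number of drop-outs with a task score is 0 in both cases.

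**Step 5. The most that the other rule could recover.** Suppose every drop-out attended. With two-sided 5% significance and 80% power (both assumed), the detectable standardized difference is approximately √(1/n₁ + 1/n₂) × (1.96 + 0.84).

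- 7 vs 28: √(1/7 + 1/28) × 2.80 = 1.18 SD (1.22 with the t distribution)
- 14 vs 21: √(1/14 + 1/21) × 2.80 = 0.97 SD (1.00 with the t distribution)

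Over a wider assumed range of 10% to 50%, the non-completer group would be 4 to 18 Veterans and the t-based figure 1.53 to 0.98 SD. The contrast would be estimable, but only large differences would be detected reliably.

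**The case against.** The best reply is that section 4.a is shorthand for the usual case. Its sentence follows directly on the description of the first visit and says that the subject will be scheduled. At that point treatment has not begun and nobody has dropped out, so every subject is to be booked. The sentence is also garbled, which makes it weak ground for an eligibility rule. Other text points the same way: section 3 allows for non-completion, and the chart review placed after the second visit collects early termination, an item of little use if early leavers were never seen. The timeline puts the assessment and the collection of early drop-out in the same row.

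Most of this stands. It shows that the intention was probably to see non-completers. It does not remove the conflict, because the Procedures section is the natural working text for staff and gives them no instruction for a Veteran who has left.

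Three stronger readings are tempting, and the protocol does not support them:

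- **That section 4.a restricts the visit to completers, so drop-outs would never be booked.** It contains no such restriction. It omits non-completers; it does not exclude them.
- **That all the adherence hypotheses lose their comparison group.** They concern adherence, which is wider than completion. Only the drop-out contrast would be empty.
- **That slow completers would be tested after Day 35.** Section 7 describes a four-week program and the timeline ends treatment at Day 28. No extended course is described.

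It is also fair to say that Veterans who have left may not return whatever the wording, so the number gained is unknown.

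**Conclusion.** The inconsistency is real and is in the current text, and it bears on a named outcome of Aim 1. Its consequence is conditional. If section 4.a is followed literally, no early drop-out has a task score at any drop-out rate, the early-drop-out part of Aim 1 cannot be tested, and the other task-adherence associations rest on a more adherent subset. If sections 3 and 4.b are followed, all of the approximately 35 Veterans are due for testing.

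The range of 7 to 14 unscored Veterans depends on an assumed drop-out of 20% to 40%, which is not a protocol figure. The point is worth correcting before enrolment because scores that were not collected cannot be recovered later. It does not invalidate Aim 1 as a whole.

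**What to change.** Bring section 4.a into line with section 3 and the timeline. For example: Visit 2 is scheduled for every enrolled Veteran between Day 29 and Day 35, counted from the first day of the IOP, whether or not the IOP was completed. This governs a research assessment only and changes nothing about treatment.

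Two short additions should go with it:

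- Record the actual day of the visit, so that departures from the window can be seen.
- State that non-completers who attend are included in the Aim 1 adherence analyses, keeping their completion status so that the contrast between adherent and non-adherent Veterans can be made.

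The cost is a few lines of text and some extra effort to reach Veterans who have left the program. The visit and its payment are already in the protocol.
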